A Clinical Trial of Silver Diamine Fluoride to Arrest Early Childhood Caries in Young Children

NCT04054635

Study Protocol and Statistical Analysis Plan

15 April 2019

Purpose:

To investigate the effectiveness of using silver diamine fluoride (SDF) to arrest early childhood caries in very young children randomized to different application frequency regimens. We will also study potential oral microbiome changes in children receiving SDF treatment.

Hypotheses:

1. Two applications of SDF at different frequencies will yield similar arrest rates.
2. SDF will negatively influence the population of cariogenic bacteria in the oral microbiome.

Objectives (*primary objective, †secondary objectives):

1. Determine the effectiveness of various application regimens of SDF to arrest caries*;
2. Determine potential changes to the oral microbiome in young children†; and
3. Determine the impact on early childhood oral health related quality of life†.

Methods:

Design: We propose a RCT to study the use of SDF to arrest cavitated caries lesions in primary teeth at different application regimens. Regimen 1 will be two applications of SDF four months apart, which is the protocol frequency adopted by the Winnipeg Regional Health Authority's Clinical Guideline on SDF. This frequency was used in a pilot study. Regimen 2 will be two applications of SDF six months apart (American Dental Association's [ADA] recommendation). Regimen 3 will be two applications of SDF one month apart, which is proposed in the American Academy of Pediatric Dentistry's clinical practice guideline. The ADA recently indicated that SDF should be prioritized over 5% NaFV for nonrestorative management of cavitated lesions. Thus, we will not include a control group to receive fluoride varnish as this would now be considered unethical and substandard care. However, we will attempt to follow as a comparison group those children whose parents/caregivers do not consent to SDF to manage their child's caries and only choose 5% NaFV.

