Third visit: Depending on the regimen children will return 4 months (Regimen 1), 6 months (Regimen 2), or 1 month (Regimen 3) later for their final follow-up visit. Parents/caregivers will complete a follow-up questionnaire administered by interviewer. Caries lesions that were treated with applications of SDF will be assessed to see if caries is arrested. Caries lesions will be assessed for colour change, size, and clinical hardness. We will also record dmft, dmfs, and PUFA scores. Clinical data will be recorded on the Clinical Record Form.

Clinical data from baseline and each follow-up visit will be linked with questionnaire data. Data will be entered into a REDCap database and saved on the secure server at CHRIM.

Oral Microbiome Sub-Study: SDF may inactivate cariogenic bacteria in vitro. There was only one study that conducted RNA analysis of plaque in six children before and after treatment (3 receiving SDF and 3 placebo) reporting no changes in relative abundance of cariogenic bacteria. In that study, not only was sample size a major limitation, but the lead author is a director of Advantage Arrest™. Our proposal to assess 30 children would provide statistical power and help elucidate if SDF leads to changes in the oral bacteriome and mycobiome. This will provide novel insights into SDF's mechanism of action, whether antimicrobial, remineralization, or both. Ten children from each regimen will have plaque samples collected. Samples will be obtained at baseline (prior to SDF application), at the first follow-up visit (prior to SDF application), and at the final visit. Nucleic acid isolation from plaque samples will be done using the DNeasy

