PowerSoil Kit (Qiagen). It allows the isolation of genomic DNA (gDNA) from fungi and Gram (+-) bacteria, which will be used for downstream analyses. For the 16S rRNA (bacteriome) and ITS1 rRNA (mycobiome) amplicon sequencing, isolated gDNA will be used for PCR amplification of the V4 region of the bacterial 16S rRNA gene, and for PCR amplification of the fungal Internal Transcribe Spacer 1 (ITS1) rRNA gene. gDNA will be sequenced at Génome Québec using paired-end Illumina MiSeq PE250 sequencing. Data analysis will be performed in the [name] lab using established methods. Briefly, demultiplexed raw sequencing results will be filtered and clustered into operational taxonomic units (OTUs) and alpha and beta diversity analyses performed using QIIME2 (Quantitative Insights into Microbial Ecology) v. 2018.11. 16S sequences will be aligned and taxonomy assigned with the HOMD database. ITS1 sequences will be aligned and taxonomy assigned with the UNITE database.

Data Analysis:

This study will estimate the success of different SDF. Descriptive statistics will be used (e.g. frequencies, proportions, and means \pm standard Deviations). The “arrest rate” (primary outcome) will be calculated for the second visit and again at the third and final visit. Bivariate analyses will assess changes in clinical measures and survey data from baseline to the follow-up. McNemar’s test will be used to compare the arrest rate between the second and third clinical visits and to compare dichotomous data from the baseline questionnaire with that from the follow-up questionnaire within each regimen. Chi-squared analysis will compare arrest rates between the regimen groups. Paired t-test will be used to compare normally distributed interval data from the baseline questionnaire with that from the follow-up questionnaire within regimens (Mann-Whitney test if not normally distributed). We will rely on repeated measures analysis of variance to assess changes in ECOHIS scores and other continuous data over time (i.e. baseline vs. second visit vs. final study visit) within each regimen group and to assess differences between regimen groups. Although this is a pilot RCT, we will explore potential changes in the oral microbiome of those randomized to different regimens. This will provide insights into potential mechanisms of SDF action, whether it has antimicrobial activity and influences the oral microbiome composition. A p value ≤ 0.05 will be significant.

Ethics:

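### No specified analysis tests Hypothesis 2: the diversity measures named do not show whether cariogenic bacteria fell, and 16S data give shares, not load

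*Combined protocol and SAP*

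**What the plan says.** The Hypotheses section is directional and names a group of organisms: "SDF will negatively influence the population of cariogenic bacteria in the oral microbiome". The matching secondary objective is looser: "Determine potential changes to the oral microbiome in young children".

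The Oral Microbiome Sub-Study takes plaque from ten children per regimen at baseline and at both follow-up visits. The bacterial assay is "PCR amplification of the V4 region of the bacterial 16S rRNA gene", with a separate ITS1 amplification for fungi. Reads are to be "clustered into operational taxonomic units (OTUs) and alpha and beta diversity analyses performed using QIIME2". The text then adds that "16S sequences will be aligned and taxonomy assigned with the HOMD database", with UNITE used for the fungal reads. No measure of total bacterial quantity is described.

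Data Analysis says only that "we will explore potential changes in the oral microbiome of those randomized to different regimens". It expects this to show whether SDF is antimicrobial, and the sub-study section hopes to separate an antimicrobial mechanism from remineralization. No cariogenic taxa are listed, and no taxon-level endpoint or test is given.

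**The concern.** The hypothesis asks whether particular bacteria fell. Alpha diversity summarises richness and evenness within a sample and ignores which taxon is which. Beta diversity measures how far apart two samples are and carries no direction for any taxon. A clear beta-diversity result would therefore fit a fall or a rise in cariogenic bacteria equally well.

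There is a second gap between measurement and conclusion. Sequencing counts show each taxon's share of the reads. An agent that reduced all plaque bacteria by the same fraction would leave the shares unchanged, so an unchanged profile could not be used against an antimicrobial mechanism. That mechanism is one of the questions the sub-study is meant to answer.

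Without a list of taxa fixed in advance, the organisms reported as cariogenic could also be chosen after the data are seen.

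**Working it through.** **1. The plan's own figure.** Ten children in each of three regimens gives 10 × 3 = 30, as stated. The sub-study section claims statistical power for this number but gives no effect size, SD or power value, so the claim cannot be reproduced.

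**2. Diversity has no direction for cariogenic taxa.** The plan names no index; Shannon, H = −Σ p ln p, and Bray-Curtis on shares, ½ Σ|p − q|, serve as examples. Take assumed profiles with the cariogenic taxon first.
- Before (0.4, 0.3, 0.2, 0.1) and after (0.1, 0.3, 0.2, 0.4): H = 1.280 both times, although the cariogenic share drops from 40% to 10%.
- Bray-Curtis is (0.30 + 0.30)/2 = 0.30, and it is also 0.30 if the two profiles are reversed.
- For a swap of 20% and 5%, Bray-Curtis is (0.15 + 0.15)/2 = 0.15 in either direction.

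**3. Share is not load.** Let s be the baseline cariogenic share, a the fractional fall in cariogenic bacteria and b the fractional fall in the others:

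share after = s(1 − a) / [s(1 − a) + (1 − s)(1 − b)]

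The documents give none of these values, so all are assumed. With the cariogenic load halved (a = 0.5):

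| Fall in other bacteria | Share after, s = 5% | s = 20% | s = 40% |
|---|---|---|---|
| 0% | 2.6% | 11.1% | 25.0% |
| 25% | 3.4% | 14.3% | 30.8% |
| 50% | 5.0% | 20.0% | 40.0% |
| 75% | 9.5% | 33.3% | 57.1% |

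The cariogenic load falls by half in every cell, yet the share falls, stays put or rises. It rises only when the other bacteria lose a larger fraction than the cariogenic ones. Two further cases start from 10 cariogenic units in 100:
- A uniform 90% kill gives 1/10 = 10%, no change in share.
- A 30% kill of cariogenic and 50% of other bacteria gives 7/(7 + 45) = 13.5%.

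**4. What the planned data could support.** For a within-child change in a taxon-level measure, at 80% power and two-sided 0.05, the detectable change in SD units is (1.960 + 0.842)/√n, and for two regimens of n each it is (1.960 + 0.842)·√(2/n). The 20% loss is stated for the main trial and is assumed to apply here: 30 × 0.8 = 24.

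| Comparison | Normal | t distribution |
|---|---|---|
| 30 children pooled | 0.51 | 0.53 |
| 24 children pooled | 0.57 | 0.60 |
| one regimen of 10 | 0.89 | 1.00 |
| two regimens of 10 | 1.25 | 1.33 |

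A pooled test of a moderate change is feasible. Comparison between regimens could detect only very large differences.

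**5. Choosing taxa afterwards.** As an illustration, testing 20 independent taxa at 0.05 gives a chance of at least one false positive of 1 − 0.95^20 = 64%.

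**6. Timing.** From the visit descriptions, baseline to final visit spans 4 + 4 = 8 months, 6 + 6 = 12 months or 1 + 1 = 2 months in Regimens 1, 2 and 3.

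**The case against.** The strongest reply is that the data to test the hypothesis are already planned. OTU counts with HOMD taxonomy give the relative abundance of named bacteria at three visits. Relative abundance is also the scale that the sub-study section uses when it describes an earlier study as "reporting no changes in relative abundance of cariogenic bacteria", and the word population in Hypothesis 2 is not defined as load. This stands. A reader might infer that Hypothesis 2 cannot be tested at all, and the documents do not support that. The test is feasible on shares; it is not specified.

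A reader might also infer that the results will be read backwards. Nothing in the plan says that a beta-diversity shift will count as support, or that an unchanged profile will count against an antimicrobial effect. The kill fractions above are assumed and act as if immediate, whereas samples come 1, 4 or 6 months after an application. The reversal of share against load is therefore a conditional risk, not a forecast.

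Two further replies carry less weight. The analysis summary is presented as brief, and Data Analysis names "repeated measures analysis of variance to assess changes in ECOHIS scores and other continuous data over time", which could take in taxon shares. Neither identifies the taxa or the endpoint that answers the hypothesis. The exploratory label limits the severity, but this is one of only two stated hypotheses and a secondary objective.

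**Conclusion.** The point holds in this form: no specified analysis tests Hypothesis 2, and the planned assay cannot establish an absolute fall in cariogenic bacteria or an antimicrobial effect on load. That diversity measures lack direction follows from their definitions. That share can differ from load is a property of compositional data; how far they would differ here is unknown, because every baseline share and kill fraction used above is an assumption.

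This is more than missing detail, since the analyses named do not answer the hypothesis stated and an unchanged composition would not support the mechanism conclusion the plan hopes to draw. It should be corrected, but its weight is limited: 30 children, a secondary objective in a pilot, and no effect on the primary arrest-rate result.

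**What to change.** In the Oral Microbiome Sub-Study and Data Analysis sections:
- List in advance a short set of cariogenic bacterial taxa.
- Make the main microbiome endpoint the within-child change from baseline to the final visit in the log-ratio of that set to all other bacterial taxa. Use 16S/HOMD data only; fungal reads come from a separate amplification and share no common denominator with the bacterial reads.
- Test it two-sided at 0.05 and report the estimate, its sign and a 95% CI, so that a rise would be detected as readily as a fall.
- Put regimen in the model, because the final visit falls at about 8, 12 or 2 months.
- Keep alpha and beta diversity and the ITS1/UNITE results as descriptive.

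In Hypotheses, restate Hypothesis 2 as a fall in the relative abundance of cariogenic bacteria. Where mechanism is discussed, state that unchanged composition is not evidence against antimicrobial action and that a change in share is not a change in load. The rewording is needed as well as the endpoint: in the 30%/50% example the log-ratio itself rises, ln[(7/45)/(10/90)] = ln 1.4 = 0.34, while the cariogenic load falls. If a claim about load is wanted, a quantity measure has to be added.

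The cost is one analysis on data already to be generated, some wording, and a narrower claim: relative, not absolute, change.

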Arrest of caries lesions will be determined by assessing clinical hardness, colour change, and size of lesions at baseline, at second visit, and at the final study visit. Children will be recruited and we will perform block randomization by site in order to achieve equal proportions in each regimen by clinic site of recruitment. Study visits will occur at the Children's Hospital Research Institute of Manitoba (CHRIM) or at community-based dental clinics. Following informed consent the child's parent/caregiver will complete a short questionnaire (via interview) on general and dental health, oral hygiene, dietary intake of sugars, and family demographics along with the ECOHIS to assess OHRQL. SDF will be applied on the day of recruitment to cavitated lesions involving dentin followed by 5% NaFV. Depending on which frequency regimen children are randomized to, they will return for a second visit. During this second visit, caries lesions treated with SDF at baseline will be assessed to see if caries is arrested as determined through measures of hardness, colour change, and size. At this same visit a second application of SDF will be applied to these initially treated caries lesions followed by 5% NaFV. Children and parents will return for the third and final study visit according to the schedule of their randomized grouping. Parents/caregivers will complete a follow-up questionnaire similar to the

baseline tool. Caries lesions previously treated by SDF will be assessed for clinical hardness, colour change and size to determine if they have arrested.

Population: As ECC is age specific, participants will be < 72 months of age with active caries and their parents/caregivers. The majority will be recruited from community-based dental clinics in Winnipeg (i.e., Access Downtown, Mount Carmel Clinic, and SMILE Plus Children's Dental Clinic) or who are currently on a wait list for dental surgery under general anesthesia in Winnipeg. We found that these were ideal sites for our recently completed feasibility trial of SDF. We will restrict participation to children living in the Winnipeg region or within a one hour drive of Winnipeg to minimize the risk of loss-to-follow-up. Eligibility criteria are designed to select young children who have active caries, and thus are at an increased risk of morbidity from existing caries and onset of new caries.

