Sample and Justification of Sample Size: Sample size for this pilot study has been determined in discussion with [name] (collaborator, Professor & Biostatistician). Our intent is to compare arrest rates between groups and to see whether the three different regimens will yield arrest rates within a range of what we will determine to be clinically acceptable. Based on our recent pilot feasibility study of SDF with 40 children (with 239 lesions) we reported an arrest rate of approximately 96% following two applications of SDF. Results from a recent systematic review state that 80% of lesions can arrest because of SDF. We believe that a range of arrest rates from 80% to 96% yield similar beneficial outcomes in the clinical setting. Based on our pilot study, 40 children had 239 lesions (average 6 lesions/child). With our pilot sample of 239 lesions, it is possible to estimate an arrest rate with a 95% confidence interval to be accurate within $\pm 6.5\%$. With 400 lesions anticipated in our proposed recruitment sample, the 95% confidence interval for the arrest rate would be $\pm 5.0\%$. We propose three SDF regimen groups and anticipate that each group will have 22 children anticipating an average of six lesions. This would mean 396 lesions would be followed in this study. We anticipate that with 400 lesions the percent of arrest will be within $\pm 5\%$ if we have 22 children in each group. To deal with potential drop-outs and loss-to-follow-up of up to 20% we will over recruit by into each group and recruit 28 per group. We anticipate that we can successfully recruit 10 children each month.

Instrumentation and Outcome Measures: Baseline and follow-up visit questionnaires will be a modified versions of those used in our SDF pilot feasibility study (developed by [name] [collaborator] in her SDF efficacy study). The questionnaire collects child and family

demographic information, oral hygiene and use of toothpaste, dietary habits (i.e., snack foods and drinks), consumption of fluoridated water, appearance of the teeth, and symptoms (e.g., pain). The tools also include sections for the parent/caregiver to complete with their child on how the child believes their teeth look and feel and how they rated their visit and SDF treatment.

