The Early Childhood Oral Health Impact Scale (ECOHIS) will be used to assess changes in OHRQL from baseline to completion of study. ECOHIS is a validated tool for use with parents/caregivers of children < 72 months of age. It consists of 13 questions grouped into two sections: 1) child impact, and 2) family impact. The child impact section includes nine questions in four areas: 1) symptoms, 2) functions, 3) psychology, and 4) self-image and social interaction. The family impact component covers two areas: 1) parental distress and 2) family function. Each question is scored from 0 to 5 [0= never, 1= hardly ever, 2= occasionally, 3 = often, 4= very often, 5= don't know]. A total score for each child is calculated by summing up response codes. The ECOHIS will allow us to calculate and compare mean ECOHIS scores at each visit and between groups. Our team has experience with analyzing ECOHIS.

Clinical outcomes assessed will include the proportion of teeth arrested (i.e., "arrest rate" = total number teeth arrested / total number of teeth treated), the proportion of children with any arrested caries, associated morbidity (dental pain and, dental abscess assessed using the PUFA index), and proportion of children requiring dental surgery under GA. The PUFA index is a score of the consequences of severely decayed teeth with visible pulpal involvement (P/p), ulceration caused by dislocated tooth fragments (U/u), fistula (F/f) and abscess (A/a). We will also record dmft and dmfs scores for each child at baseline and at subsequent study visits. The dmft and dmfs scores are cumulative counts of the total number of primary teeth or surfaces decayed, missing due to, or filled because of caries.

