Our research staff will contact interested parents/caregivers and will inform them of the study objectives, eligibility criteria, and procedures. Children will undergo a dental screening by the principle investigator or a calibrated and trained dental examiner to determine whether children meet the clinical criteria for this study by having cavitated caries lesions involving dentin (i.e. ICDAS category 5 or 6). Since ECC is more common in disadvantaged populations, we will arrange for transportation (i.e., taxis) for participants. We also anticipate that some participants will be newcomers and will require interpreters. We will arrange for WRHA interpreters when needed. Visits will occur at the principle investigator's dental suite at CHRIM or at one of the community-based clinics.

Baseline visit: Following written informed consent, children will be randomly allocated into one of three groups using sealed envelopes to ensure random allocation. Parents/caregivers will complete the baseline questionnaire administered by interviewer. Children will undergo a dental examination (without x-rays) to record the number of teeth and tooth surfaces with caries meeting ICDAS 5 or 6 criteria and the specific tooth numbers. We will record the location, size, hardness, colour, and activity status of each eligible caries lesion. We will also assess the total number of primary teeth and tooth surfaces affected by caries (i.e., dmft and dmfs). We will also determine the PUFA index. SDF will then be applied with a microbrush for one minute to each cavitated lesion meeting the eligibility criteria followed by 5% NaFV.

Second visit: Depending on the regimen children will return 4 months (Regimen 1), 6 months (Regimen 2), or 1 month (Regimen 3) later for their first follow-up visit and second application of SDF. Parents/caregivers will complete the ECOHIS tool. Prior to the second application of SDF, caries lesions that received the first application of SDF will be assessed to determine if caries is arresting. Lesions will be assessed for colour change, size, and hardness. Clinical data will be recorded including dmft, dmfs, and PUFA scores will be recorded. Following the dental assessment of the lesions under investigation, SDF will be applied to these lesions for one minute followed by 5% NaFV.

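### Children are randomised, but the chi-squared test of the primary arrest rate treats each child's teeth as independent; its true size is about 7–30% (four teeth per child) or 9–44% (six) at assumed ICCs of 0.05–0.5

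*Combined protocol and SAP*

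**What the plan says.** **Unit of randomisation: the child.** The baseline visit text (Implementation) says "children will be randomly allocated into one of three groups using sealed envelopes". The Design section adds that "we will perform block randomization by site in order to achieve equal proportions in each regimen by clinic site of recruitment".

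**Unit of the primary outcome: the tooth.** Instrumentation and Outcome Measures defines the arrest rate as "total number teeth arrested / total number of teeth treated". The Data Analysis section names it the primary outcome and calculates it at the second and third visits.

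**Test.** In the Data Analysis section: "Chi-squared analysis will compare arrest rates between the regimen groups". The significance threshold is p ≤ 0.05. McNemar's test compares the arrest rate between the second and third visits.

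**Sample size.** The plan expects that "each group will have 22 children anticipating an average of six lesions", counts 396 lesions as the sample, and states: "With 400 lesions anticipated in our proposed recruitment sample, the 95% confidence interval for the arrest rate would be" ±5.0%. For the 239 pilot lesions it gives ±6.5%.

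The document names no ICC, design effect, robust variance, GEE or mixed model. One child-level outcome is listed, "the proportion of children with any arrested caries", but it is separate from the primary arrest rate.

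**The concern.** An ordinary chi-squared test is valid only if the counted units are independent. A child whose first tooth arrests is more likely to have the second arrest too, because both share the same saliva, diet, hygiene and cooperation with treatment. The sample then carries less information than its tooth count suggests, and the test rejects too often.

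Two conclusions are exposed. First, the p ≤ 0.05 rule would declare equal regimens different more than 5% of the time. Second, Hypothesis 1 is that the regimens give similar arrest rates, and the sample-size section regards anything from 80% to 96% as similarly beneficial. Support for similarity has to come from interval width, and an interval that ignores the child is too narrow. The results are meant to inform a scaled-up trial.

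**Working it through.** **Inputs from the document.** Three regimens; 22 evaluable children each; six lesions per child (239/40 = 5.98); 3 × 22 × 6 = 396 lesions; alpha 0.05. Arrest rates run from 80% to 96%; of the pilot, the plan says "we reported an arrest rate of approximately 96% following two applications of SDF".

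**Assumed, because the document gives no value.** ICC 0.05, 0.1, 0.3 and 0.5. Treated teeth per child m = 4 or 6: the plan's six counts lesions, and one tooth can carry more than one lesion. A third case has unequal counts with mean 6 and coefficient of variation (CV) 0.7.

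**1. The plan's own precision.** The binomial half-width with independent lesions at p = 0.5 is z√(0.25/n). With z = 1.96 it is 4.9 points (n = 400) and 6.3 (n = 239). With z = 2 it is 1/√n, or 5.0 and 6.5, the stated figures. The sample size therefore treats lesions as independent.

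**2. Size of the three-group test.** The design effect is DE = 1 + (m − 1) × ICC, and size = P(χ²₂ > 5.991/DE) = 0.05^(1/DE). For m = 6 and ICC 0.3, DE = 1 + 5 × 0.3 = 2.5 and size = 0.05^(0.4) = 30.2%. The simulated ranges are from beta-binomial data with 22 children per regimen, equal true arrest of 80, 90 or 96%, and 20,000 runs.

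| ICC | m = 4: DE | formula | simulated | m = 6: DE | formula | simulated | unequal counts, simulated |
|---|---|---|---|---|---|---|---|
| 0.05 | 1.15 | 7.4% | 6.6–7.5% | 1.25 | 9.1% | 8.4–9.4% | 10.3–11.4% |
| 0.1 | 1.30 | 10.0% | 8.8–10.0% | 1.50 | 13.6% | 13.0–13.7% | 16.8–18.1% |
| 0.3 | 1.90 | 20.7% | 19.2–20.9% | 2.50 | 30.2% | 29.1–30.3% | 36.4–40.3% |
| 0.5 | 2.50 | 30.2% | 28.3–30.7% | 3.50 | 42.5% | 43.1–44.5% | 49.5–54.7% |

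A single two-regimen comparison (1 df) is less inflated: 6.8–21.5% for m = 4 and 8.0–29.5% for m = 6.

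**3. Interval width.** Intervals are too narrow by √DE: 1.1 to 1.6 for m = 4 and 1.1 to 1.9 for m = 6. For unequal counts DE = 1 + (6 × 1.49 − 1) × ICC, which runs from 1.40 to 4.97, a factor of 1.2 to 2.2. The half-width of a regimen difference is 1.96 × √(2p(1 − p) × DE/(22m)), in points:

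| m, arrest rate | independent | ICC 0.1 | ICC 0.3 | ICC 0.5 |
|---|---|---|---|---|
| 6, 80% | 9.7 | 11.8 | 15.3 | 18.1 |
| 6, 96% | 4.7 | 5.8 | 7.5 | 8.8 |
| 4, 80% | 11.8 | 13.5 | 16.3 | 18.7 |
| 4, 96% | 5.8 | 6.6 | 8.0 | 9.2 |

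The range the plan accepts as similar is 96 − 80 = 16 points wide.

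**4. The stated ±5% for 400 lesions.** With m = 6, 1.96 × √(p(1 − p) × DE/400) reaches 5 points at ICC 0.125 for 80% arrest and at ICC 0.378 for 90%. It never does at 96%.

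**5. McNemar between visits** (22 children × 6 lesions, 80% arrest, 10,000 runs). Size stays near 5% if each child's effect is stable over visits. At the four ICCs it is 6%, 8%, 16% and 23% if half the children get a new effect, and 8%, 11%, 22% and 30% if all do. McNemar on questionnaire items has one pair per child and is unaffected.

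**The case against.** - **The size rests on assumptions.** This stands: the percentages are ranges, not estimates. At the low end the inflation is modest, and 30–44% needs an ICC of 0.5, for which the document gives no support. But every ICC examined puts the size above 5%, and zero correlation within a mouth is the least plausible value.
- **It is a pilot whose hypothesis is similarity.** False differences would count against that hypothesis, and the plan specifies no interval for a regimen difference. The harm through narrow intervals is therefore conditional on how similarity is argued. Even so, the plan sets a significance threshold for this comparison, and the threshold is wrong.
- **The sample size has a cushion.** This stands. Because p = 0.5 was used, clustering does not break the stated ±5% at the pilot's 96%. The case rests on the test, not on that figure.
- **The replacement is elaborate.** In part. One child-clustered model would also cure the defect and is accepted below. Permuting within site also disregards the randomisation blocks, whose sizes the document does not give.
- **The robust difference interval is weak when exactly one regimen of a pair has no non-arrests.** Simulated coverage in those runs, with both true rates at 96%, was 67% (m = 4, ICC 0.05; 6.8% of runs) and 56% (m = 6, ICC 0.1; 2.6% of runs). These are rare outcomes: overall coverage at equal 96% rates is 95–98.6%. Extending the square-and-add method to them does not close the gap, since it covers 59–81% in those runs at ICC 0.05. It remains a disclosed limitation.

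**Conclusion.** The concern holds and must be fixed before analysis. The primary between-regimen test is invalid as written, because the analysis unit is the tooth, the randomised unit is the child, and nothing links the two. The nominal 5% three-group test has a true size of about 7–30% with four teeth per child and 9–44% with six. Unequal counts raise it to about 10–55%. This rests on 22 children per regimen, exchangeable correlation within a child, and assumed ICCs of 0.05 to 0.5. The between-visit McNemar test of lesions is affected only if a child's lesions change together. Pilot status lowers the stakes without repairing the test.

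**What to change.** Replace the chi-squared sentence in the Data Analysis section with:

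> The primary comparison is the arrest rate at the final visit. It will be compared between regimens by a permutation test that re-allocates whole children among regimens within recruitment site, using the Pearson chi-squared statistic of the pooled tooth counts. Pairwise regimen differences will be reported with 95% confidence intervals clustered on child (robust variance, t reference). Each regimen's arrest rate will be reported with a 95% Wilson interval in which the number of teeth is divided by a design effect estimated by pooling the three regimens. If both regimens of a pair have no non-arrests, the interval for their difference will be formed from their two Wilson intervals by the square-and-add (Newcombe) method.

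Also state:
- that the final visit is a choice, since the plan calculates the rate at both visits;
- the degrees of freedom of the t reference;
- the design effect: summed child-clustered variances of the arrested counts over summed binomial variances, not below 1. If every tooth in all regimens arrests, use the number of children as the effective number;
- that the second and third visits will be compared by testing the within-child change with the same child-clustered variance.

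Do not use the plain robust t interval for a single regimen: at 96% arrest it covers only 70–88%. A child-clustered logistic GEE or mixed model with small-sample correction is an acceptable, simpler alternative, but it is also weak when a regimen has no non-arrests.

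**Performance.** In simulation with three assumed sites, the permutation test had size 2.9–5.3%. The robust difference interval covered 93.7–98.6% at equal rates and fell to 91% at unequal rates (ICC 0.5, CV 0.7). The pooled-design-effect Wilson interval covered 92.5–97.1%.

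**Cost.** New wording and somewhat more analysis; no extra data or visits. Intervals widen by about 1.1 to 1.9, or up to about 2.2 with unequal counts. If true arrest is 80/88/96% with six teeth per child, power is about 91%, 85%, 64% and 48% at ICC 0.05, 0.1, 0.3 and 0.5.
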